### **3.5.2. Laboratory Data**

Safety laboratory tests will be performed as described in the protocol.

To determine if there are any clinically significant laboratory abnormalities, the haematological, clinical chemistry (serum) and urinalysis safety tests will be assessed against the criteria specified in the sponsor reporting standards. The assessment will not take into account whether each subject's baseline test result is within or outside the laboratory reference range for the particular laboratory parameter.

The baseline measurement is the pre-dose measurement on Day -1.

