	Visit Identifier Abbreviations used in this table may be found in Appendix 9: Abbreviations.	Screening									Trea	tment	Perio	d				Notes
2023 04:36 (GMT)	Appendix 7. Appreviations.			Peri	od 1		Pe	riod 2		P	eriod	3		Period	14	Follow-up Contact	Early Termination/ Discontinuation	Follow-up contact will occur by telephone and must occur 28 to 35 days after the last administration of ritlecitinib.
3 04:36	Days Relative to Day 1	Day -28 to Day -2	Day -	Day 1	Day 2	Day 3	28-35 Days after last dose in Period 4											
202;	Study Day	-28 to -2	-1	1	2	3	4	5	6	7	8	9	10	11	12			
ce19\Approved\Approved On: 15-Nov-5	Physical examination	X	X			X			X			X			X		X	Complete (full) physical examination must either be conducted at Screening or upon Admission on Day -1 of Period 1 only; brief physical examination will be performed on Day 3 of each period or at early termination/discontin uation, and as needed per investigator discretion if there are findings during the previous examination, new/open adverse events.

	Visit Identifier Abbreviations used in this	Screening									Trea	tment	Perio	d				Notes
	table may be found in Appendix 9: Abbreviations .																	
2023 04:36 (GMT)				Peri	od 1		Pe	riod 2		P	eriod	3		Period	d 4	Follow-up Contact	Early Termination/ Discontinuation	Follow-up contact will occur by telephone and must occur 28 to 35 days after the last administration of ritlecitinib.
4:3	Days Relative to Day 1	Day -28 to		Day	Day 2	Day 3	Day	Day 2	Day 3	Day	Day 2	Day 3	Day	Day 2	Day 3	28-35 Days after last dose in Period		
30		Day -2	1	1	2	3	1	Z	3	1	Z	3	1	Z	3	4		
202	Study Day	-28 to -2	-1	1	2	3	4	5	6	7	8	9	10	11	12			
pproved\Approved On: 15-Nov-	Safety laboratory	X	X			X			X			X			X		X	• Participants should fast for at least 4 hours prior to any safety blood collection. Additional laboratory assessments may be performed if deemed necessary by the investigator. Refer to Table 5 in Section 10.2. Day 3 safety labs of every period to be done after PK blood sampling.
9\A	Demography, height and weight	X																

	Visit Identifier Abbreviations used in this table may be found in Appendix 9: Abbreviations.	Screening									Trea	tment	Perio	d					Notes
2023 04:36 (GMT)				Peri	iod 1		Pe	riod 2		P	eriod	3		Period	14	Follow-up Contact	Early Termination/ Discontinuation	•	Follow-up contact will occur by telephone and must occur 28 to 35 days after the last administration of ritlecitinib.

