Of the 16 SAEs, 12 were considered by the investigator as unrelated to study intervention. The 4 SAEs that were considered related to study intervention in the opinion of the investigator were sepsis and empyema (both in 1 participant); breast cancer; and eczema. There were no deaths in the study.

Treatment with ritlecitinib was associated with changes in hematological parameters, some of which were dose dependent. In the first weeks of the study, there were slight, transient decreases in hemoglobin and small, variable changes in neutrophil and leukocyte levels. Small, early decreases in platelets were observed with ritlecitinib treatment; these levels remained stable up to Week 48. Dose-dependent early decreases in absolute lymphocyte levels, T lymphocytes (CD3) and T lymphocyte subsets (CD4 and CD8) were observed. There was a dose-dependent early decrease in CD16/56 (NK cells), particularly in groups who had received a 200 mg loading dose of Ritlecitinib for 4 weeks. Overall, there were no clinically meaningful effects of ritlecitinib on ALT, AST, bilirubin, or alkaline phosphatase. The incidence of elevation in hepatic enzymes was low and not dose dependent. Up to Week 48, there were no potential Hy's law cases.

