- 18. Standard 12-lead ECG that demonstrates clinically relevant abnormalities that may affect participant safety or interpretation of study results (eg, QTcF > 450 ms, complete LBBB, signs of an acute or indeterminate- age myocardial infarction, ST-T interval changes suggestive of myocardial ischemia, second- or third- degree AV

block, or serious bradyarrhythmias or tachyarrhythmias). If QTcF exceeds 450 ms, or QRS exceeds 120 ms, the ECG should be repeated twice, and the average of the 3 QTcF or QRS values should be used to determine the participant's eligibility. Computer interpreted- ECGs should be overread by a physician experienced in reading ECGs before excluding a participant.

- 19. Participants with ANY of the following abnormalities in clinical laboratory tests at screening or Day -1, as assessed by the study-specific- laboratory and confirmed by a single repeat test, if deemed necessary:
 - AST or ALT level $> 1.5 \times ULN$;
 - Total bilirubin level >1.5 × ULN; participants with a history of Gilbert's syndrome may have direct bilirubin measured and would be eligible for this study provided the direct bilirubin level is ≤ ULN;
 - Hemoglobin level <120 g/L (12.0 g/dL);
 - Platelet count $<150 \times 10^9/L (150,000 \text{ cells/mm}^3);$
 - ANC $<1.2 \times 10^9/L$ (1200 cells/mm³);
 - ALC $< 0.8 \times 10^9 / L (800 \text{ cells/mm}^3);$
 - eGFR <60 mL/minute/1.73 m² based on the CKD-EPI equation

In the opinion of the investigator or Pfizer (or designee), have any clinically significant laboratory abnormality that could affect interpretation of study data or the participant's participation in the study.

Other Exclusion Criteria:

- 20. History of alcohol abuse or binge drinking and/or any other illicit drug use or dependence within 6 months of Screening. Binge drinking is defined as a pattern of 5 (male) and 4 (female) or more alcoholic drinks in about 2 hours. As a general rule, alcohol intake should not exceed 14 units per week (1 unit = 8 ounces (240 mL) beer, 1 ounce (30 mL) of 40% spirit, or 3 ounces (90 mL) of wine).
- 21. Blood donation (excluding plasma donations) of approximately 1 pint (500 mL) or more within 60 days prior to dosing.
- 22. Use of tobacco/nicotine containing products in excess of 5 cigarettes/day.
- 23. History of severe allergic or anaphylactic reactions.

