### 3.4. Baseline Variables

**Start and end dates of study treatment:** The date of first dose (start date) of study treatment is the earliest date of non-zero dosing of the study drug. The date of last dose of study treatment is the latest date of non-zero dosing of the study drug.

**Definition of baseline:** For vital signs and ECG, the baseline measurement of Periods 1-3 is the last pre-dose measurement taken on Day 1 of Period 1, and the baseline measurement of Period 4 is the last pre-dose measurement taken on Day 1 of Period 4. For safety labs, the baseline measurement is the pre-dose measurement on Day -1.

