## **6.6. Safety Summaries and Analyses**

A set of summary tables split by treatment will be produced to evaluate any potential risk associated with the safety and toleration of administering ritlectinib as PO solution, MR1, or MR2 formulation.

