### **6.6.2. Laboratory Data**

Laboratory data will be listed and summarized by treatment in accordance with the sponsor reporting standards. The baseline measurement is the pre-dose measurement on Day -1.

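### By-treatment laboratory tables can count one persistent or pre-existing abnormality under several treatments, and Period 4 (fed) labs follow four doses against a mean of two for each fasted treatment

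*SAP*

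**What the plan says.** - **Timing of samples.** The safety laboratory row of the Schedule of Activities (Protocol 1.3) has samples at screening, on Day -1 and on Day 3 of each period, that is, study days 3, 6, 9 and 12. The note reads "Day 3 safety labs of every period to be done after PK blood sampling". Periods 2 to 4 have no separate pre-dose lab.
- **Baseline.** SAP 3.4: "For safety labs, the baseline measurement is the pre-dose measurement on Day -1". SAP 3.5.2 and 6.6.2 repeat this. For vital signs and ECG, by contrast, SAP 3.4 sets a new baseline on Day 1 of Period 4.
- **Flagging.** SAP 3.5.2 applies criteria from the sponsor's reporting standards, which are not reproduced, and adds: "The assessment will not take into account whether each subject's baseline test result is within or outside the laboratory reference range".
- **Presentation.** SAP 6.6.2: "Laboratory data will be listed and summarized by treatment in accordance with the sponsor reporting standards". SAP 6.6 introduces the safety output with "A set of summary tables split by treatment will be produced to evaluate any potential risk" and names solution, MR1 and MR2. It does not say whether fed dosing has its own column.
- **Design.** Table 2 (Protocol 4.1, SAP 2.3) gives one dose per period. Periods 1 to 3 are fasted and Period 4 is fed.

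**The concern.** A Day 3 lab in Period k follows k doses, but a by-treatment table assigns it wholly to the treatment given in Period k. With one pre-study baseline and no regard to baseline status, nothing in the stated rule separates a finding that began under the current treatment from one that began earlier or was there before any drug.

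The 3-day washout is justified in Protocol 4.2 by plasma concentration. That argument does not show that a laboratory value has recovered after an irreversible inhibitor. The protocol lists reduced lymphocyte and platelet counts among the identified risks (section 1.1, ethical considerations). From the alopecia areata trial it reports "Dose-dependent early decreases in absolute lymphocyte levels", although under repeated daily dosing.

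Laboratory tests are a named part of the secondary objective on the safety and tolerability of MR1 and MR2. What is at stake is whether a reader can tell which treatment a flagged abnormality belongs to.

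**Working it through.** **Inputs.** Six sequences with 2 participants each (Protocol 9.5 and Table 2), one dose per period (Protocol 6.1), labs on Day -1 and on Day 3 of each period. Check on the plan's own figure: 6 × 2 = 12 participants, as stated.

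**Step 1: doses received by the Day 3 lab.** Each of A, B and C falls in Period 1, 2 and 3 for 4 participants each. Fed treatments fall only in Period 4.

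| Treatment | Participants | Doses by the Day 3 lab | Mean | With an earlier dose |
|---|---|---|---|---|
| A, B or C fasted (each) | 12 | 1, 2 or 3 | (4×1 + 4×2 + 4×3)/12 = 2.0 | 8 of 12 |
| B fed or C fed (each) | 6 | 4 | 4.0 | 6 of 6 |

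If fed and fasted were pooled by formulation, MR1 and MR2 would each average (12×2 + 6×4)/18 = 2.67 doses, against 2.0 for solution. The protocol calls the treatment letters representative. Exchanging the letters does not change the fasted means or the four doses before a fed lab.

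**Step 2: how often one abnormality is counted.** Assume that it persists to study day 12 and meets the sponsor's criteria throughout, and that fed is a separate column. Onset in Period k is counted 5 − k times:

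- Period 1: 4; Period 2: 3; Period 3: 2; Period 4: 1.
- Mean, if onset is equally likely in each period: (4 + 3 + 2 + 1)/4 = 2.5.
- Already present on Day -1: 4.

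An abnormality that has resolved by the next Day 3 lab is counted once.

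**Step 3: effect of position alone.** Let q be a small onset probability, the same in each period and for each treatment, with full persistence. The proportion flagged at the Day 3 lab of Period k is about kq. Averaged over periods, this is (q + 2q + 3q)/3 = 2q for a fasted treatment and 4q for a fed one, about twofold. With no persistence it is q in both. The documents do not say where between these the truth lies.

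**Step 4: order among the fasted treatments.** Whenever a fasted treatment has a predecessor, B follows A, C follows B and A follows C (8 of 12 each). If A caused a persistent abnormality in everyone, it would also be counted under B in 8/12, C in 4/12, and each fed treatment in 6/6. For B or C as the cause, the fasted pattern rotates.

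**Step 5: findings that predate dosing.** Exclusion criterion 19 removes the main liver, haematology and renal abnormalities at screening or Day -1. It makes an exception for Gilbert's syndrome: such participants "may have direct bilirubin measured and would be eligible for this study provided the direct bilirubin level is" within the normal limit. If raised total bilirubin meets the sponsor's criteria, such a participant can be flagged in all four periods. Criterion 19 sets no numeric limit for urinalysis or eosinophils.

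**The case against.** The case for leaving the plan alone has real strength.

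- **Persistence is not shown.** A reader might infer that every earlier abnormality is charged to every later treatment. That holds only if it is still present at each later Day 3 lab. The lymphocyte finding comes from a trial with up to 48 weeks of treatment. Protocol 2.3 and 4.3 report no clinically significant laboratory changes in the studies they cite, which include single doses up to 800 mg and multiple doses up to 400 mg. This stands.
- **A biased food comparison might be inferred.** The SAP specifies no fed-versus-fasted laboratory comparison and names no fed column, and the food-effect objective concerns PK exposure. One event shown as 1/12 (8%) under a fasted treatment and 1/6 (17%) under a fed one also partly reflects denominators. What remains is that any reading of Period 4 labs is a reading after four doses.
- **A bias between formulations from dose number might be inferred.** A, B and C each average 2.0 doses, so the documents do not support it. Only the cyclic order in Step 4 is unbalanced.
- **Other outputs help.** Labs are listed individually for 12 participants. Investigators record clinically significant changes as AEs (Protocol 8.3.4), and events that started before the first dose are not treatment-emergent (SAP 3.5.1). These help a careful reader but do not correct the summary table.
- **Day -1 is the only drug-free lab after screening.** Replacing it with the preceding Day 3 value would make a post-dose value the baseline. A slow decline would be charged to the period in which it crosses a threshold, and recovery could look like an effect. This stands, and it is why the Day -1 baseline should be kept.

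**Conclusion.** The concern holds in limited form. Followed as written, the SAP counts a pre-existing abnormality, or one that persists across periods, under more than one treatment: up to four times if it lasts throughout. Period 4 labs follow four doses in participants dosed in all periods, against a mean of two for each fasted treatment. The design figures are exact for 12 participants who complete all periods. The repeat counts rest on persistence and on the unseen sponsor criteria, and the twofold figure also needs a small, constant onset probability.

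The consequence is confined to descriptive attribution in one part of a secondary safety objective. There is no hypothesis test, and the primary PK analysis and the sample size are unaffected. A reader might go further and conclude that the laboratory results will mislead about a formulation or about food. The documents do not support that, because they give no size or duration for any shift at this dosing. The change is still worth making, because it is cheap and the safety objective names laboratory tests.

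**What to change.** Keep the Day -1 baseline and the planned by-treatment table. In SAP 3.4, 3.5.2 and 6.6.2, add:

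1. A by-treatment count limited to abnormalities that are new or worsened relative to both Day -1 and the last lab before that period's dose. For Period 1 the two coincide. For Periods 2 to 4 the second is normally the preceding period's Day 3 sample. A persistent, unchanging abnormality is then counted once, and an unchanged pre-existing one not at all. Requiring both references stops a return to the Day -1 level from being counted.
2. A summary of change from Day -1 by study day (3, 6, 9 and 12), presented as the cumulative effect and not by treatment.
3. A separate column for fed (Period 4) labs, with a note that they follow four doses.

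The cost is SAP wording and one or two extra tables; every sample is already scheduled. One limitation remains. Under the Schedule of Activities the preceding Day 3 sample falls the day before the next dose, or earlier if the participant is discharged between periods, so it may still carry some effect of the earlier dose. The study-day table would show this. The additions do not separate food from period in Period 4, which is why the note is needed.

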### **3.5.3. Vital Signs**

Supine blood pressure and pulse measurements will be taken at all time points listed in the Schedule of Activities given in the protocol.

For calculation of change from baseline for Periods 1 - 3, the baseline of Period 4 is used as post-baseline; for Period 4, the measurement on Day 3 will be used as the post-baseline measurement.

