3 04:30	Days Relative to Day 1	Day -28 to Day -2	Day -	Day 1	Day 2	Day 3	28-35 Days after last dose in Period 4												
202,	Study Day	-28 to -2	-1	1	2	3	4	5	6	7	8	9	10	11	12				
On: 15-Nov-	Pregnancy test (WOCBP only)	X	X															•	Given that the participant will be confined in CRU for the entire study, if tested negative on admission, no further test is needed.
pproved\Approved	Contraception check	Х	X													X	X	•	The contraception check is to confirm that contraception, if applicable, is used consistently and correctly.
Srov	Review prior or concomitant treatments and medications	X	X	\rightarrow	X	X													
ce19\Apr	FSH (WONCBP only)	X																•	Serum FSH for confirmation of postmenopausal status only
$\tilde{\infty}$	Urine drug testing	X	X																
7e19f2	Supine 12-lead single ECG	X		X			X			X			X		X		X		Day 1 ECG to be done pre-dose.

Visit Identifier Abbreviations used in this table may be found in Appendix 9: Abbreviations.	Screening									Trea	itment	Perio	d				Notes
Days Relative to Day 1 Study Day			Peri	od 1		Pe	riod 2		P	eriod	3		Period	14	Follow-up Contact	Early Termination/ Discontinuation	Follow-up contact will occur by telephone and must occur 28 to 35 days after the last administration of ritlecitinib.
Days Relative to Day 1	Day -28 to Day -2	Day -	Day 1	Day 2	Day 3	28-35 Days after last dose in Period 4											
Study Day	-28 to -2	-1	1	2	3	4	5	6	7	8	9	10	11	12			
Supine blood pressure, pulse rate and temperature	X		X			X			X			X		X		Х	Day 1 vital signs are collected prior to pre- dose (baseline) blood drawn.
HIV, HBsAg, HBcAb, HCVAb QuantiFERON®TB Gold test or equivalent	X																If HBsAg is negative and HBcAb is positive, HBsAb should be evaluated.
QuantiFERON®TB Gold test or equivalent	X																
Study intervention administration Pharmacokinetic blood sampling			X			X			X			X					Please refer to Section 5.3.2 for details regarding dosing under fed and fasted state.
Pharmacokinetic blood sampling			X	X	X	X	X	X	X	X	X	X	X	X		Х	PK sample collection will be done pre-dose and at times post-dose as shown in Table 1 below.

	Visit Identifier Abbreviations used in this	Screening									Trea	tment	Perio	d				Notes
	table may be found in																	

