4. STUDY DESIGN

4.1. Overall Design

This is a single dose, open-label randomized, 4-period, 6-sequence crossover study in a single cohort of approximately 12 healthy male and/or female participants randomized to one of the sequences (containing 1 solution and 2 MR [MR1 and MR2] capsule formulations of ritlecitinib) displayed in Table 2 where the treatment names A; B & C are representative. The first 3 periods are under fasted condition and the fourth period is under fed condition to

investigate food effect on the PK of modified release formulations MR1 and MR2. Dosing in each treatment period will be separated by at least 3 days to minimize any carryover effect. The study includes standard inpatient monitoring of study participants following single oral doses. Standard safety laboratory tests and urinalysis both before and after dosing will assess participant safety, while intensive blood draws following ritlecitinib administration will provide PK exposure data to characterize the relative bioavailability and absorption rate from different formulations. Normal venous PK blood samples for PK analysis will be collected pre-dose and at times specified in the SoA. For a given participant, the total study duration from screening to follow-up phone call will be between approximately 8 and 11 weeks. Participants may be discharged between periods at the discretion of PI.

Participants who discontinue prior to completion of the study for reasons unrelated to safety may be replaced at the discretion of the PI and the sponsor. Participants withdrawn for safety reasons will not be replaced.

Table 2. Study Design and Treatments

Sequence	Period 1	Period 2	Period 3	Period 4
1 (n=2)	A	В	С	B, fed
2 (n=2)	В	С	A	B, fed
3 (n=2)	С	A	В	B, fed
4 (n=2)	A	В	С	C, fed
5 (n=2)	В	С	A	C, fed
6 (n=2)	С	A	В	C, fed

Treatment A: ritlecitinib 100 mg PO solution

Treatment B: ritlecitinib 100 mg (2×50 mg) MR1 capsules Treatment C: ritlecitinib 100 mg (2×50 mg) MR2 capsules

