7.2. Participant Discontinuation/Withdrawal From the Study

A participant may withdraw from the study at any time at their own request. Reasons for discontinuation from the study include the following:

- Refused further follow-up;
- Lost to follow-up;
- Death;
- Study terminated by sponsor;
- Participant meeting protocol specified criteria for discontinuation.

At the time of discontinuation from the study, if possible, an early discontinuation visit should be conducted. See the SoA for assessments to be collected at the time of study discontinuation and follow-up and for any further evaluations that need to be completed.

The early discontinuation visit applies only to participants who are enrolled/randomized and then are prematurely withdrawn from the study. Participants should be questioned regarding their reason for withdrawal.

The participant will be permanently discontinued from the study intervention and the study at that time.

If a participant withdraws from the study, they may request destruction of any remaining samples taken and not tested, and the investigator must document any such requests in the site study records and notify the sponsor accordingly.

If the participant withdraws from the study and also withdraws consent (see Section 7.2.1) for disclosure of future information, no further evaluations will be performed and no additional data will be collected. The sponsor may retain and continue to use any data collected before such withdrawal of consent.

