### **3.5.4. ECG**

Single supine 12-lead ECG will be taken at all time points listed in the Schedule of Activities given in the protocol. For calculation of change from baseline for Periods 1 - 3, the baseline of Period 4 is used as post-baseline; for Period 4, the measurement on Day 3 will be used as the post-baseline measurement.

The QT, QTc, PR, QRS and heart rate will be recorded at each assessment time.

If not supplied, QTcF will be derived using Fridericia's heart rate correction formula:

$$QTcF = QT / (RR)^{1/3} \quad \text{where RR} = 60/\text{HR} \text{ (if not provided)}$$

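### ECG and vital-sign change scores rest on one fixed post-baseline reading per block, so a dosed participant who stops before it falls out of the change tables and change-based categories, although an early-termination reading is planned

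*SAP*

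**What the plan says.** SAP 3.4 sets two baselines for ECG and vital signs. For the fasted block, "the baseline measurement of Periods 1-3 is the last pre-dose measurement taken on Day 1 of Period 1". For the fed period, "the baseline measurement of Period 4 is the last pre-dose measurement taken on Day 1 of Period 4".

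SAP 3.5.3 (vital signs) and 3.5.4 (ECG) then name one post-baseline value per block. For the first block: "For calculation of change from baseline for Periods 1 - 3, the baseline of Period 4 is used as post-baseline". For the second: "for Period 4, the measurement on Day 3 will be used as the post-baseline measurement".

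SAP Appendix 1 has two kinds of limit. The absolute limits cover QTcF, PR, QRS, blood pressure and pulse. The change-based limits cover QTcF increase (>30-60 and >60 msec), PR and QRS percentage increase, and systolic and diastolic change of at least 30 and 20 mm Hg. Measurements meeting any of these are to be listed in the study report.

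The protocol's Schedule of Activities (1.3) marks both the ECG row and the row for "Supine blood pressure, pulse rate and temperature" under Early Termination/Discontinuation. Protocol 7.2 supports this: "At the time of discontinuation from the study, if possible, an early discontinuation visit should be conducted". On replacement, protocol 4.1 says: "Participants withdrawn for safety reasons will not be replaced". Participants who leave for other reasons may be replaced.

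Protocol 9.3.3.1 asks for ECG changes by treatment and time, and for counts of participants, by treatment, according to their highest postdose QTc and their largest rise from baseline. SAP 2.1 states that modifications to the protocol's analysis plan are not applicable.

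**The concern.** The safety analysis set (SAP section 4) is everyone who took at least one dose. The change rule has a narrower reach. The Periods 1-3 change exists only for participants who have a Period 4 Day 1 reading, and the Period 4 change only for those who have a Period 4 Day 3 reading. A participant dosed once, twice or three times and then stopped has a baseline and, in most cases, a later reading, but no change score.

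Safety withdrawals are among those who can be lost this way, and they are not replaced. ECG and vital signs belong to a stated secondary objective, and the change-based limits decide in part what is listed as meeting the criteria of potential clinical concern. A gap that can depend on a safety event should be closed when the data to close it are already being collected.

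**Working it through.** The plan states no figure for this point, so there is none to reproduce. The check sets the schedule against the SAP rule and then counts.

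**Step 1: which readings exist and what the SAP does with them.** The ECG and vital-sign rows of the Schedule of Activities mark the same columns. For ECG the note reads "Day 1 ECG to be done pre-dose".

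| Scheduled reading | Role in the SAP change score |
|---|---|
| Screening | none |
| Period 1 Day 1, pre-dose | baseline for Periods 1-3 |
| Period 2 Day 1, pre-dose (after one dose) | none |
| Period 3 Day 1, pre-dose (after two doses) | none |
| Period 4 Day 1, pre-dose (after three doses) | post-baseline for Periods 1-3; baseline for Period 4 |
| Period 4 Day 3 | post-baseline for Period 4 |
| Early termination | none |

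**Step 2: who has a change score.**

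- Stops after dosing in Period 1, 2 or 3 and does not reach Period 4: the baseline is present and the Period 4 Day 1 value is absent, so no change can be calculated for Periods 1-3.
- Dosed in Period 4 but leaves before Day 3: the Periods 1-3 change is available and the Period 4 change is not.
- Reaches Period 4 Day 3: both changes are available.

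**Step 3: size of each loss.** Planned N is 12, two in each of six sequences (protocol 9.5). If k participants stop before Period 4 and are not replaced, the number evaluable is 12 - k and the fraction lost is k/12:

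- k = 1: 11 evaluable, 1/12 = 8.3% lost
- k = 2: 10 evaluable, 2/12 = 16.7% lost
- k = 3: 9 evaluable, 3/12 = 25.0% lost

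If early-termination readings were admitted, up to 12 of 12 would have a change value, provided that visit takes place.

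**Step 4: do the absolute limits cover the gap?** Only in part. The lowest absolute QTcF category begins above 450 msec. A rise of more than 60 msec stays at or below 450 whenever the later value is 450 or less, which requires a baseline below 450 - 60 = 390 msec. Such a participant meets the severe change category but no absolute QTcF category.

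**Step 5: the two documents side by side.** A largest rise from baseline, as protocol 9.3.3.1 asks for, on its ordinary meaning draws on every available post-dose ECG. The SAP takes one fixed reading per block, and its Periods 1-3 block pools solution, MR1 and MR2. That is a modification of the protocol analysis, and SAP 2.1 does not declare it.

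**The case against.** The case that this matters little is a fair one, and much of it stands.

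**The participant stays visible.** An abnormal ECG or vital sign that leads to discontinuation must be recorded as an adverse event (protocol 10.3.1). Protocol Appendix 8 names a QTcF rise above 60 ms as a possible adverse event. SAP 6.5.1 reports discontinuations by treatment, and SAP 6.6.3 and 6.6.4 list the data. With 12 participants, open label and no hypothesis testing, a safety withdrawal would be seen individually. A reader might infer that the rule makes the overall safety result look cleaner. The documents do not support that; the omission is limited to the change tables and the change-based categories.

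**The schedule limits what could be missed.** A reader might picture someone stopped in Period 2 for a QTcF rise above 60 ms who then vanishes from the table. No post-dose ECG is scheduled within Period 1, 2 or 3, so a within-period rise there could appear only on an unscheduled or early-termination ECG. The example is possible but is not the expected route.

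**These are not completers-only tables.** For Periods 1-3, anyone with a Period 4 Day 1 reading counts, whether or not they finish.

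**No probability can be attached.** With an assumed any-cause risk of stopping p, the chance of losing at least one of 12 is 1 - (1 - p)^12: 21.5%, 46.0% and 71.8% for p = 2%, 5% and 10%. The documents give no such risk. Any-cause stopping also includes non-safety withdrawals, who may be replaced, so these figures do not measure a loss related to safety.

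**Other SAP text might fill the gap.** SAP 5.3 defers missing safety data to sponsor imputation rules, and SAP 6.6.3 and 6.6.4 speak of summaries at each planned time point. The sponsor rules are not shown, and nothing says that they substitute an early-termination value. The wording on time points conflicts with the single-value rule. Both leave the question open.

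**The SAP may depart from the protocol.** Protocol section 9 allows it. The departure still needs to be declared.

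**Conclusion.** The point holds in a limited form. As written, SAP 3.5.3 and 3.5.4 give no ECG or vital-sign change for a dosed participant who stops before the one designated reading, so that participant cannot be counted in the change-based categories of Appendix 1. The early-termination reading, and the Period 2 and 3 Day 1 readings that also follow dosing, have no role in the change score.

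Each unreplaced loss before Period 4 is 1 of 12, or 8.3%, of the planned participants in the Periods 1-3 change summaries. How often this would happen cannot be said from the documents. Primary pharmacokinetic results are unaffected. The conclusion assumes that the unseen sponsor standards do not already bring the early-termination reading into the change score. It is a cheap improvement to the safety reporting and also brings the SAP closer to protocol 9.3.3.1.

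**What to change.** In SAP 3.5.3, 3.5.4 and Appendix 1, state the following:

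- The change-based categories use the worst post-dose reading available. This includes early-termination readings, unscheduled readings, and the Period 2 and Period 3 Day 1 readings.
- An early-termination reading is counted in the block where dosing stopped (Periods 1-3 or Period 4), against that block's baseline, with the last treatment received and the time since dose given in a footnote.
- The descriptive means keep the planned readings only, with the number evaluable shown for each block. Putting early-termination values into the means would mix times after dose, and labelling them by last treatment would not fit summaries made by block.

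Reconcile SAP 2.1 with protocol 9.3.3.1: either restore the largest QTc increase by treatment or declare the departure. Align the wording on planned time points in SAP 6.6.3 and 6.6.4 with the rule chosen.

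The cost is a few SAP sentences and minor programming, since the scheduled data are already collected. Two limits remain. Readings in the categories will fall at different times after dose, and because the early discontinuation visit is not guaranteed, some participants may still lack a value.
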